6.2.5.5. Urine Drug Screen

A urine sample for the following assessments will be collected at Screening (Visit 1): amphetamines, barbiturates, benzodiazepines, cocaine, opiates, phencyclidine, and tetrahydrocannabinol.

6.2.5.6. Columbia Suicide Severity Rating Scale (C-SSRS)

The C-SSRS is a prospective assessment tool routinely used in studies of drugs with any potential for CNS effects. It captures the occurrence, severity, and frequency of suicide-related thoughts and behaviors during the assessment period. For patients aged 7 to 17 years and if the developmental level is appropriate, the questionnaire will be completed at Baseline (Visit 3) and Visit 10 (Week 13) or the Early Withdrawal Visit.

6.2.6. Adverse Events and Serious Adverse Events

6.2.6.1. Definition of Adverse Events

An AE is defined as any untoward medical occurrence in a patient administered a pharmaceutical product during the course of a clinical investigation. An AE can therefore be any unfavorable

and unintended sign, symptom, or disease temporally associated with the use of an investigational product, whether or not thought to be related to the investigational product.

Patients will be monitored throughout the study for AEs. Monitoring for treatment-emergent AEs (TEAEs) will begin as soon as the patient is dosed. All AEs must be followed until they are resolved or stabilized, or until all attempts to determine resolution of the event are exhausted. The investigator should use their discretion in ordering additional tests as necessary to monitor the progress of such events.

An AE may be:

- A new illness, not documented in the patient's medical history;
- Worsening of a concomitant illness;
- An effect of the study medication; it could be an abnormal laboratory value, as well as a significant shift from baseline within normal range which the qualified investigator or medical qualified designate considers to be clinically important;
- A combination of two or more of these factors.

Surgical procedures themselves are not AEs. They are therapeutic measures for conditions that require surgery. The condition for which the surgery is required is an AE, if it occurs or is detected during the study period. Planned surgical measures permitted by the clinical study protocol and the condition(s) leading to these measures are not AEs, if the condition(s) was (were) known before the start of study treatment. In the latter case, the condition should be reported as medical history.

Weight gain or loss will not be recorded as an AE. Hyperphagia behaviors and skin picking will not be recorded as AEs; however, any other behaviors may be recorded as AEs based on the Investigator's opinion.

Patients will be monitored throughout the study for AEs. All AEs must be followed until they are resolved or stabilized, or until all attempts to determine resolution of the event are exhausted. The investigator should use his/her discretion in ordering additional tests as necessary to monitor the progress of such events.

Adverse events reported prior to dose administration will be recorded as part of the patient's medical history.

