In an open label study of Epidiolex[®] (a plant-derived purified CBD), 214 patients suffering from different refractory epilepsies were enrolled between January 15, 2014, and January 15, 2015 (Devinsky et al., 2016). Patients were given oral cannabidiol at 2-5 mg/kg per day, up-titrated until intolerance or to a maximum dose of 25 mg/kg or 50 mg/kg per day (dependent on study site), for a 12-week treatment period. Titration to a maximum dose of 50 mg/kg per day was done in 48 (30%) patients, 23 of whom received a dose of more than 25 mg/kg per day during the 12-week treatment period. Of the 214 enrolled patients, 162 (76%) patients who had at least 12 weeks of follow-up after the first dose of cannabidiol were included in the safety and tolerability analysis, 137 (64%) patients were included in the efficacy analysis.

The most common adverse events reported (in more than 10% of patients) were somnolence (n=41, 25%), decreased appetite (n=31, 19%), diarrhea (n=31, 19%), fatigue (n=21, 13%), and convulsion (n=18, 11%). Five (3%) patients discontinued treatment because of an adverse event. Serious adverse events were reported in 48 (30%) patients, including one death—a sudden unexpected death in epilepsy regarded as unrelated to study drug; 20 (12%) patients had severe adverse events possibly related to cannabidiol use, the most common of which was status epilepticus (n=9 [6%]).

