Hyperphagic behaviors can also be dangerous in persons who are not obese, with increased risks of death due to choking while sneaking food, and gastric perforations after consuming more food than usual (Dykens et al., 2007). Approximately 8% of deaths in individuals with PWS was reported due to the choking, especially on hot dogs (Stevenson et al., 2007). Prader-Willi Syndrome patients also are known to eat discarded (contaminated) food and items that are not for human consumption such as pet food, or even non-food items such as paint or paper (Griggs et al., 2015).

Subjects with PWS continue to experience a significant unmet medical need, especially when it comes to hyperphagia behavior and obesity. There are no approved drugs currently to treat these behaviors. Fenfluramine demonstrated significant efficacy in Prader-Willi Syndrome patients but was removed from the market due to cardiac valve concerns. Rimonabant was approved in the EU for obesity and a trial was ongoing in Prader-Willi Syndrome. However, the drug was never approved in the US and removed from the market in the EU due to significant psychiatric side effects. A trial in PWS, while demonstrating a trend for efficacy was terminated early for safety concerns. Currently, Zafgen's product Beloranib demonstrated significant positive effects on weight loss and hyperphagia behavior in patients with Prader-Willi syndrome but is currently on hold due to two deaths that were thought to be caused by thrombotic events. Orlistat, lorcaserin, Qsymia, and Contrave have been approved for obesity but not studied in the Prader-Willi Syndrome population. Therefore, there continues to be a high unmet need for an efficacious and safe treatment for this population.

Cannabidiol has been safely administered to over 300 medically complex children and was generally well-tolerated. The adverse events recorded do not correspond to those encountered by previous trials in patients with Prader-Willi syndrome. The anxiolytic effects of CBD and its indirect effect on the CB1 receptor suggest an improved side effect profile in this population.

In conclusion, there is both pre-clinical and clinical evidence that affecting the endocannabinoid system with cannabidiols, including cannabidiol, may demonstrate a clinically relevant effect on

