6.2.6.4. Definition of Serious Adverse Events

A serious AE (SAE) is any AE that fulfills any of the following criteria, as per 21 CFR 312.32:

- Results in death;
- Is life-threatening;
- Requires in-patient hospitalization or prolongation of existing hospitalization;
- Results in persistent or significant disability or incapacity;
- Is a congenital anomaly or birth defect;
- Is medically significant or requires intervention to prevent one of the outcomes listed above.

Serious AEs will be captured from the time of consent through the end of the study.

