6.2.6.7. Adverse Event Recording and Reporting

Adverse events will be recorded throughout the study in the source documents and in the CRFs. The investigator will rate AEs for seriousness, intensity, causality, action taken, and outcome as described in the previous section.

Expedited reporting is required for serious unexpected adverse drug reactions. Fatal or life-threatening unexpected drug reactions must be reported by the Sponsor to regulatory agencies no more than 7 days after the Sponsor's first knowledge of the reaction; followed by as complete a report as possible within 8 additional days. Unexpected adverse drug reactions must be reported no later than 15 days after the Sponsor's first knowledge of the reaction. In order to comply with these requirements, the investigator or delegate must inform the Sponsor immediately upon occurrence of any SAE. The site will complete the SAE Report Form as thoroughly as possible and e-mail it to Insys or designee within 24 hours of the investigators first knowledge of the event. Details will be provided in the safety monitoring plan.

These SAE reports must contain the following information:

- A. Study name/number
- B. Study drug
- C. Investigator details (name, phone, fax, e-mail)
- D. Patient number
- E. Patient initials
- F. Patient demographics
- G. Clinical event
 - 1) Description
 - 2) Date of onset

- 3) Treatment (drug, dose, dosage form)
 - 4) Adverse event relationship to study drug
 - 5) Action taken regarding study drug in direct relationship to the AE
- H. If the AE was fatal or life-threatening
- I. Cause of death (whether or not the death was related to study drug)
- J. Autopsy findings (if available)

The Sponsor or its representative will be responsible for notification to regulatory agencies.

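### The AE exemption for weight change, hyperphagia behaviors and skin picking has no exception for serious events, so some serious events have no required SAE route

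*Protocol*

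**What the plan says.** Protocol Section 6.2.6.1 opens with a broad AE definition that takes in the worsening of an existing illness and effects of the study drug. It then makes an exemption: "Weight gain or loss will not be recorded as an AE. Hyperphagia behaviors and skin picking will not be recorded as AEs". The sentence goes on to give the investigator discretion, but only over what remains: "however, any other behaviors may be recorded as AEs".

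Section 6.2.6.4 builds seriousness on top of AE status: "A serious AE (SAE) is any AE that fulfills any of the following criteria, as per 21 CFR 312.32". One of the criteria is "Requires in-patient hospitalization or prolongation of existing hospitalization".

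Section 6.2.6.7 sets the reporting duty: "the investigator or delegate must inform the Sponsor immediately upon occurrence of any SAE". The SAE form follows within 24 hours of the investigator learning of the event.

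SAP Section 7.7.2 codes and tabulates the AEs that have been entered on the eCRF, including the treatment-emergent serious ones (TESAEs).

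**The concern.** The exemption has a sensible purpose. Weight and hyperphagia are efficacy measures here, and coding every fluctuation as an AE would add noise. But the wording is unconditional, and the exempt terms lie in the domain the drug is meant to act on. The protocol's background treats hyperphagia as the most life-threatening feature of the syndrome and refers to "increased risks of death due to choking while sneaking food, and gastric perforations after consuming more food than usual". It also reports reduced appetite as a common event on another cannabidiol product.

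The population is children aged 8 to 17. If a child were admitted for marked weight loss, or for dangerous food-seeking, and no other diagnosis were made, a site following the text would have no instruction to record or report it. The sponsor would get no prompt notice and no causality rating, and the comparison of serious events between arms would not include it. Sites might also resolve the tension with the general AE definition differently, which would make the safety data uneven.

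**Working it through.** The plan gives no figure on this point, so there is nothing to reproduce. The check is to put the sections side by side and follow one event through them.

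**1. Is the exemption limited?** Section 6.2.6.1 does not limit it by severity, cause, hospitalisation or outcome. The investigator's discretion reaches only behaviors other than those named. The same section's exclusion of surgical procedures makes a useful contrast: there, a condition that needs surgery still counts as an AE if it arises or is found during the study. The exemption for weight, hyperphagia and skin picking has no clause of that kind.

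**2. Can an event be an SAE without being an AE?** Not under Section 6.2.6.4, which selects SAEs from among AEs. Hospitalisation makes an AE serious; it does not make a non-AE into an AE.

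**3. Does anything else trigger notice?** Section 6.2.6.7 attaches immediate and 24-hour notice to the term SAE.

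**4. Is there an exception elsewhere?** None was found in Protocol Sections 6.2.6.1 to 6.2.6.9, Protocol Section 8.6.4.1, or SAP Sections 6.2 and 7.7.2.

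**5. Does the gap carry into the analysis?** Yes. The TEAE and TESAE tables in SAP Section 7.7.2 are built from AEs recorded on the eCRF, so an event never entered cannot appear.

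**6. What is captured in other ways?**

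| Event or data | Covered by the exemption? | Route the documents require |
|---|---|---|
| Admission for marked weight loss, no other diagnosis | Yes | None as AE or SAE |
| Admission for dangerous food-seeking, no other diagnosis | Yes | None as AE or SAE |
| Choking, gastric perforation, infected skin lesion | No | AE, and SAE if serious |
| Decreased appetite | No | AE, and SAE if serious |
| Weight by visit | Not applicable | Summaries with minimum and maximum, and listings (SAP Sections 7.1, 7.7.4) |
| HQ-CT by visit | Not applicable | Efficacy model, summaries and listings (SAP Sections 7.1, 7.6.1) |
| Reason for withdrawal | Not applicable | CRF entry and disposition table (Protocol Section 3.4, SAP Section 7.2) |

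Weight and HQ-CT are measured at each visit from Screening to Visit 10 (Protocol Sections 6.1.1 and 6.1.2). The documents attach no seriousness assessment, causality rating or expedited report to those values. Table 1 schedules neither measure at Visit 11, so they do not cover the taper and follow-up weeks.

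**The case against.** The strongest reply is that little is lost.

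- **The named hazards stay reportable.** Choking and perforation are medical events and not behaviors, and the exemption does not name them. This stands, and it confines the gap to events with no separate diagnosis.
- **Weight remains in the safety output.** SAP Section 7.7.4 summarises weight and BMI in the Safety population, and minimum and maximum are standard statistics under SAP Section 7.1, so an extreme loss at a visit would show. This stands too. A reader might infer that weight harm vanishes from the safety comparison, and the documents do not support that. What is missing is the event-level record and the prompt notice.
- **Withdrawals are still explained.** The reason goes on the CRF and into the disposition table, and Protocol Section 5.2 asks sites for information on lack of efficacy and on drop-outs. This stands, but it is not SAE reporting.
- **No sentence says that serious cases are exempt.** True. The loss of the SAE route is inferred from nested definitions, and a cautious investigator might report such an admission anyway. A reader might conclude that these events are forbidden from being reported. The supportable reading is that reporting is not required and that the literal wording points away from it.
- **A specific exception to a general definition is not a contradiction.** That is fair, and excluding non-serious change already measured as efficacy is a legitimate design choice. The weakness is only that the exception has no limit at seriousness.

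A reader might also try to size the gap from the decreased-appetite rate in Protocol Section 1.3.3 (31 of 162 patients, 19%): 0.19 × 33 = 6.3 patients in the active arm. That does not measure what is lost. Decreased appetite is not an exempt term, and the rate comes from an open-label epilepsy study of a plant-derived product. Section 1.3.3 does not list it among the most common events in the sponsor's own studies.

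**Conclusion.** The concern holds in a narrow form. Followed literally, Protocol Sections 6.2.6.1, 6.2.6.4 and 6.2.6.7 together leave an event whose only term is weight change, hyperphagia behavior or skin picking without a required AE or SAE route, even when it meets a seriousness criterion. The SAP's TEAE and TESAE tables inherit the omission.

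The size is unknown: the documents give no rate of serious events confined to these terms, and it may be small. The conclusion rests on two assumptions: that sites apply the exemption as written, and that no CRF guideline or safety monitoring plan outside these documents restores the route. It does not bear on the primary efficacy analysis. It deserves correction because the exempt terms lie in the drug's target domain, the patients are children, and the remedy is cheap.

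**What to change.** Reconcile Section 6.2.6.1 with Section 6.2.6.4 by adding one sentence after the exemption, for example:

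> *This exemption does not apply to any event that meets a criterion in Section 6.2.6.4; such events are recorded as AEs and reported as SAEs.*

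Align the CRF completion guidelines. SAP Section 7.7.2 needs no new method, because the tables will pick up these events once they are on the eCRF. Keep the exemption for non-serious change already measured as efficacy. Further triggers, such as dose reduction or any medical treatment, would go beyond the gap shown here.

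The cost is one sentence in the protocol, a matching line in the guidelines, and a few extra SAE entries, some of which will reflect the disease and not the drug.

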6.2.6.2. Classification of Adverse Events

Adverse events are to be recorded on the AE page of the patient's case report form (CRF). Severity will be graded according to the following definitions:

- Mild: The patient experiences awareness of symptoms but these are easily tolerated or managed without specific treatment.
- Moderate: The patient experiences discomfort enough to cause interference with usual activity, and/or the condition requires specific treatment.
- Severe: The patient is incapacitated with inability to work or do usual activity, and/or the event requires significant treatment measures.

Action taken will be categorized as none, study drug discontinued, dose modified, required concomitant medication, required procedure, or other.

Event outcome at resolution or time of last follow-up will recorded as event resolved, resolved with sequelae, ongoing, or death.

6.2.6.3. Causality: Drug Relationship Assessment

The relationship of the event to the study drug should be determined by the investigator according to the following criteria:

- Definitely related: The event follows a reasonable temporal sequence from the time of drug administration that cannot be explained, follows a known or expected response pattern to the study drug, that is confirmed by improvement on stopping and reappearance of the event on repeated exposure and that could not be reasonably explained by other factors such as the patient's clinical condition, intercurrent illness, or concomitant drugs.
- Not related: The event is most likely produced by other factors such as the patient's clinical condition, intercurrent illness, or concomitant drugs, and does not follow a known response pattern to the study drug, or the temporal relationship of the event to study drug administration makes a causal relationship unlikely.
- Possibly related: The event follows a reasonable temporal sequence from the time of drug administration, and/or follows a known response pattern to the study drug, but could have been produced by other factors such as the patient's clinical condition, intercurrent illness, or concomitant drugs.
- Unlikely related: The event follows little or no temporal sequence from the time of drug administration that makes a causal relationship improbable and/or other factors such as the patient's clinical condition, intercurrent illness, or concomitant drugs is a more likely alternative.
- Probably related: The event follows a reasonable temporal sequence from the time of drug administration, and/or follows a known response pattern to the study drug, and cannot be reasonably explained by other factors such as the patient's clinical condition, intercurrent illness, or concomitant drugs.

6.2.6.4. Definition of Serious Adverse Events

A serious AE (SAE) is any AE that fulfills any of the following criteria, as per 21 CFR 312.32:

- Results in death;
- Is life-threatening;
- Requires in-patient hospitalization or prolongation of existing hospitalization;
- Results in persistent or significant disability or incapacity;
- Is a congenital anomaly or birth defect;
- Is medically significant or requires intervention to prevent one of the outcomes listed above.

Serious AEs will be captured from the time of consent through the end of the study.

6.2.6.5. Serious Adverse Event Actions Taken

Actions taken may consist of:

- None: No action taken
- Treatment: Standard of care measures instituted
- Drug withdrawn: Study medication was permanently discontinued because of the AE
- Unknown: Not known, not observed, not recorded, or refused

6.2.6.6. Serious Adverse Event Outcome at the Time of Last Observation

The outcome at the time of last observation will be classified as:

- Recovered/resolved
- Recovered/resolved with sequelae
- Not recovered/not resolved
- Death
- Unknown

6.2.6.7. Adverse Event Recording and Reporting

Adverse events will be recorded throughout the study in the source documents and in the CRFs. The investigator will rate AEs for seriousness, intensity, causality, action taken, and outcome as described in the previous section.

Expedited reporting is required for serious unexpected adverse drug reactions. Fatal or life-threatening unexpected drug reactions must be reported by the Sponsor to regulatory agencies no more than 7 days after the Sponsor's first knowledge of the reaction; followed by as complete a report as possible within 8 additional days. Unexpected adverse drug reactions must be reported no later than 15 days after the Sponsor's first knowledge of the reaction. In order to comply with these requirements, the investigator or delegate must inform the Sponsor immediately upon occurrence of any SAE. The site will complete the SAE Report Form as thoroughly as possible and e-mail it to Insys or designee within 24 hours of the investigators first knowledge of the event. Details will be provided in the safety monitoring plan.

These SAE reports must contain the following information:

- A. Study name/number
- B. Study drug
- C. Investigator details (name, phone, fax, e-mail)
- D. Patient number
- E. Patient initials
- F. Patient demographics
- G. Clinical event
 - 1) Description
 - 2) Date of onset

- 3) Treatment (drug, dose, dosage form)
 - 4) Adverse event relationship to study drug
 - 5) Action taken regarding study drug in direct relationship to the AE
- H. If the AE was fatal or life-threatening
- I. Cause of death (whether or not the death was related to study drug)
- J. Autopsy findings (if available)

The Sponsor or its representative will be responsible for notification to regulatory agencies.

6.2.6.8. Adverse Event Follow-Up

All non-serious AEs that are not related or unlikely to be related to study treatment will be followed until the end of study participation. All SAEs or AEs that are considered as possibly, probably, or definitely related to treatment will be followed until resolution or stabilization.

6.2.6.9. Special Considerations

Cannabidiol inhibits drug metabolism mediated by a subset of CYP proteins (see [Section 1.1.2](#)). Thus, the Investigator and study center staff should monitor patients who are taking concomitant medications that are metabolized by CYP2C19, CYP2C9, CYP2D6, CYP3A4, CYP1A2 or by P-glycoprotein with special care.

6.2.7. Pharmacokinetics Assessments

Blood draws for PK sampling will be taken at each visit during the Baseline (Visit 3), Maintenance Period (Visits 6 and 8), and Study Completion/Early Withdrawal (Visit 10).

Whole blood will be obtained in a K₂-EDTA Vacutainer[®] tube for the determination of the plasma levels of CBD and 7-OH-CBD. The blood sample will be obtained prior to study medication dosing.

